5.1 Case Record Survey SNT-IR-006 inclusion criteria

The survey will collect historically documented visual acuity data for all patients at participating sites with a genetically confirmed diagnosis of LHON. No exclusion criteria apply. Patients are not required to attend the clinic for the survey.

SNT-IV-005 Statistical Analysis Plan

Confidential

5.2 Case Record Survey SNT-CRS-002 inclusion criteria

Case Records from patients will be collected from ALL patients of the participating sites who fulfil the following prospectively defined inclusion criteria:

- Age ≥ 12 years
- The onset of symptoms is dated after 1999 and is well documented (at least month of onset of symptoms is known for each eye)
- At least two VA assessments are available within 5 years of onset of symptoms and prior to idebenone use
- Have a genetic diagnosis for LHON for one of the following mtDNA mutations: G11778A, G3460A, T14484C

5.3 Case Record Survey SNT-CRS-002 exclusion criteria

- Any participation in an interventional clinical trial after the onset of symptoms
- Any other cause of visual impairment (e.g. glaucoma, diabetic retinopathy, AIDS related visual impairment, cataract, macular degeneration, etc.) or any active ocular disorder (uveitis, infections, inflammatory retinal disease, thyroid eye disease, etc.) during the data collection period

5.4 LEROS inclusion criteria

The following criteria should be assessed during Baseline Visit. If any does not apply, the patient must not be included in the study:

- Impaired visual acuity in affected eyes due to LHON
- No explanation for visual loss besides LHON
- Age ≥ 12 years
- Onset of symptoms ≤5 years prior to Baseline
- Confirmation of either G11778A, G3460A or T14484C LHON mtDNA (for the ITT population, not required for enrolment)
- Written informed consent obtained from the patient
- Ability and willingness to comply with study procedures and visits
- Women of Childbearing Potential (WCBP) who have a negative urine or serum pregnancy test at Baseline visit and who are willing to use a highly effective contraceptive measure and maintain it until treatment discontinuation.

SNT-IV-005 Statistical Analysis Plan

Confidential

5.5 LEROS exclusion criteria

The following criteria should be checked during Baseline Visit. If any applies, the patient must not be included in the study:

- Patient has provided natural history data to the Case Record Survey (SNT-CRS-002)
- Any previous use of idebenone
- Any other cause of visual impairment (e.g. glaucoma, diabetic retinopathy, AIDS related visual impairment, cataract, macular degeneration, etc.) or any active ocular disorder (uveitis, infections, inflammatory retinal disease, thyroid eye disease, etc.)
- Known history of clinically significant elevations (greater than 3 times the upper limit of normal) of AST, ALT or creatinine
- Patient has a condition or is in a situation which, in an investigator's opinion may put the patient at significant risk, may confound study results or may interfere significantly with the patient's participation in the study
- Participation in another clinical trial of any investigational drug within 3 months prior to Baseline
- Hypersensitivity to the active substance or to any of the following excipients (as listed in section 6.1 of Raxone SmPC): Lactose monohydrate, Microcrystalline cellulose, Croscarmellose sodium, Povidone K25, Magnesium stearate, Colloidal silica, Macrogol 3350, Poly(vinyl alcohol), Talc, Titanium dioxide, Sunset yellow FCF (E110).
- Women who are pregnant or have a positive pregnancy test at Baseline visit
- Women who are breastfeeding

6 Sample size considerations

The present study is designed to provide sufficient statistical power for a pre-planned indirect comparison of the primary endpoint against an external natural history control group.

As defined in the original LEROS study protocol (Version1.0, 29 January 2016, Section 9.6), the sample size calculation for LEROS assumed an expected 24% responder rate in the external natural history control group (combined data from SNT-IR-006 and SNT-CRS-002). The protocol defines a pre-planned check of the estimate of responder rate in the control group, once the enrolment of the new natural history study (SNT-CRS-002) has been completed. In case the responder rate in the control group is different from 24%, a sample size re-calculation using the updated control group estimate can be considered.

As SNT-CRS-002 study was completed (Clinical Study Report version 1.0 dated 15 July 2019), the data collected in the natural history studies has now been checked for the estimate of the responder rate. Based on the combined data from 175 eyes in the two natural history studies (SNT-IR-006 and SNT-CRS-002), the estimated responder rate is below 22%, i.e. lower than the initially expected rate of 24%. Although the determination of the exact responder rate for the natural history studies requires final data from the LEROS study for matching purposes, it is reasonable to assume that the responder rate of the natural history studies is not higher than 22%. The sample size for LEROS study is therefore re-calculated using the same methods as in the original protocol (Version1.0, 29 January 2016). In order to reach a power of 90% for the comparison of the responder rates between the natural history studies (assumed to be 22% instead of 24%) and the LEROS study (assumed to be 40%, as defined in the protocol), evaluable data from altogether 110 eyes from the LEROS study is required. In order to account for a drop-out rate of 30% (as defined in the protocol), at least 80 patients (equal to 160 eyes) will be enrolled to the LEROS study.

The sample size calculation was done with nQuery Advisor version 8.3.

For the sample size for the eye treated >1 year after the onset of symptoms and the corresponding external natural history control group, the aim is to collect VA data from same number of eyes as for the primary objective in order to compare the patients treated ≤1 and >1 year since the onset of symptoms and to compare patients treated with Raxone >1 year since the onset of symptoms with the corresponding natural history control group, assuming sufficient natural history control data can be collected to generate the natural history control group as described in 8.3.2.

Study: SNT-IV-005

V1.0 07 June 2021

7 Statistical hypotheses

The primary aim of the analysis is to show the superiority of Raxone® (patients treated ≤1 year after onset of symptoms) versus matching NH IDE naïve patients in proportion of eyes with clinically relevant recovery of VA from BL or 12 month maintenance of BL VA better than 1.0 logMAR

H₀: Raxone® (patients treated ≤1 year after onset of symptoms) is not superior to matching NH IDE naïve patients in proportion of eyes with CRR of VA from BL or 12 month maintenance of BL VA better than $1.0 \log MAR$

 H_1 : Raxone® (patients treated ≤ 1 year after onset of symptoms) is superior to matching NH IDE naïve patients in proportion of eyes with CRR of VA from BL or 12 month maintenance of BL VA better than $1.0 \log MAR$

A two-sided 95% confidence interval (CI) for the odds ratio (Raxone® versus NH IDE naïve) is used in the evaluation of the hypotheses. Superiority is shown if the lower limit of the two-sided 95% CI is greater than 1. This is equivalent to obtaining a p-value of less than 0.05 in the statistical test for the H_0 .

8 Analysis sets

8.1 Safety Population

CRS-1 and CRS-2 did not collect any safety data.

Safety will only be assessed in LEROS patients.

The Safety Population will include all patients enrolled in the LEROS study, who received at least one dose of study medication. The Safety population will be used when evaluating safety variables.

8.2 Intent-To-Treat Population

There is no Intent-To-Treat (ITT) population defined for CRS-1 and CRS-2, and Natural History control set is defined in section 8.4.

ITT population will include all patients enrolled to LEROS which provide at least one post-BL VA assessment.

The ITT population in conjunction with the external NH control set will be used to evaluate efficacy endpoints defined in section 4.

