During the Baseline visit the diagnosis of LHON will be confirmed and other eye diseases excluded. This will require fundoscopy with dilated pupils to be performed at the Baseline visit and every 12 months thereafter. Blood sample will be taken for the genetic analysis, if the genetic diagnosis of the patient is not confirmed at the Baseline visit. The report from the genetic analysis will need to be on file prior to Visit 4.

Should the genetic diagnosis reveal that a patient does not harbour a LHON-specific mtDNA mutation, the patient will be withdrawn from the study.

It should be noted however that the VA outcomes for patients carrying one of the three major LHON-specific mtDNA mutations (G3460A, G11778A or T14484A) will be used in the primary analyses.

The following study procedures are performed at Baseline/Visit 1: physical exam, vital signs, weight, safety blood and urine sampling and a urine or serum pregnancy test for WCBP. The investigator should ensure that the results of the safety blood and urine analyses and pregnancy

test are reviewed and approved during Visit 1. The patient will be informed by the investigator or study nurse by phone should these results not be available at the day of Visit 1/Baseline.

Patients and/or parents/legal guardians will monitor safety throughout the study at home, and will document any adverse events (AEs), or other relevant findings in a patient diary.

Patient and/or the parent/legal guardian will be instructed to contact the investigator immediately should the patient manifest any signs or symptoms perceived as serious during the period extending from the day of signature of the consent form up to and including the last visit. After this period of time, the investigator should report to the sponsor only AEs that are serious and considered related to the study medication.

Information about AEs or serious adverse events (SAEs) will be collected throughout the study period and followed up as referred to in Sections 8.1 - 8.3 of this protocol.

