9.3 Analysis Populations

9.3.1 Intent-To-Treat Population

The Intent-To-Treat (ITT) population will include all enrolled patients who received at least one dose of the study medication and provide at least one post-baseline VA assessment and are confirmed carriers of only one of the three major LHON mtDNA: G11778A, G3460A or T14484C.

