9.3 Examination of subgroups

Subgroup analyses will be performed in LEROS ITT population, considering time since symptoms onset in **most** recent affected eye at BL.

These subgroups will be analysed separately for patients ≤1 year and >1 year since symptoms onset in most recent affected eye at BL:

- LHON mtDNA mutations:
 - G11778A
 - G3460A
 - T14484C
 - Any other mutation
- Age at BL:
 - < 18 years;
 - \geq 18 years and < 35 years;
 - $\geq 35 \text{ years}$
- Best VA Blindness Category (BC) at BL:
 - Off-chart: CF, HM, LP or NLP
 - Legally blind: 1.0 ≤ logMAR ≤1.68
 - Non-legally blind: logMAR < 1.0

Confidential

10 Disposition

Patients' disposition will be presented separately for LEROS and Natural History (CRS-1 and CRS-2).

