Endpoint: Proportion of eyes and patients treated with Raxone® ≤1 year after the onset of symptoms with CRR of VA from BL or in which BL VA better than 1.0 logMAR was maintained following 6, 18 and 24 months of treatment with Raxone® compared to matching external NH control group

Analysis method: This endpoint will be analysed separately for each follow-up with methods similar as for analysing the primary endpoint as defined in section The criteria of inclusion/exclusion for the pre-planned indirect comparison of the primary endpoint against an external natural history control group, where it is only considered who are carriers of only one of the three major LHON mtDNA (G11778A, G3460A or T14484C). Due this criterion, efficacy analysis where there is an indirect comparison to the external natural history control group, will be based on the mITT population.

Primary endpoint 12.1.

Endpoint: Proportion of eyes/patients treated with Raxone® ≤1 year after the onset of symptoms with "Off-chart" VA at BL in whom VA improves to better than 1.60 logMAR by Month 6, 12, 18 and 24

Analysis method: This endpoint will be analysed by means of descriptive statistics in the LEROS ITT population and presented in contingency tables with frequencies and percentages as illustrated in section 19.2.

Endpoint: Proportion of eyes/patients treated with Raxone® >1 year after the onset of symptoms with "Off-chart" VA at BL in whom VA improves to better than 1.60 logMAR by Month 6, 12, 18 and 24

Analysis method: This endpoint will be analysed by means of descriptive statistics in the LEROS ITT population and presented in contingency tables with frequencies and percentages as illustrated in section 19.2.

Endpoint: Proportion of eyes/patients treated with Raxone® \leq 1 year after the onset of symptoms with VA in the categories of better than 1.0 logMAR, 1.0 to 1.68 logMAR and above 1.68 logMAR at each assessment time point up to Month 24

Analysis method: This endpoint will by means of descriptive statistics in the LEROS ITT population and presented in contingency tables with frequencies and percentages as illustrated in section 19.2.

Endpoint: Proportion of eyes/patients treated with Raxone® >1 year after the onset of symptoms with VA in the categories of better than 1.0 logMAR, 1.0 to 1.68 logMAR and above 1.68 logMAR at each assessment time point up to Month 24

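### SAP 8.2 sets no mutation condition for ITT, against SAP 5.4 and protocol 9.3.1, so patients withdrawn as mutation-negative can enter some early descriptive LEROS-only outputs

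*SAP*

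**What the plan says.** Two documents and several sections define or imply who is in ITT.

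- SAP 8.2: "ITT population will include all patients enrolled to LEROS which provide at least one post-BL VA assessment". Neither genotype nor dosing is mentioned.
- SAP 5.4, among the LEROS inclusion criteria: "Confirmation of either G11778A, G3460A or T14484C LHON mtDNA (for the ITT population, not required for enrolment").
- Protocol 9.3.1 requires at least one dose, at least one post-baseline acuity, and patients who "are confirmed carriers of only one of the three major LHON mtDNA: G11778A, G3460A or T14484C".
- SAP 9.3 lists the three major mutations as ITT subgroups and adds "Any other mutation". Table 19-3 has a matching column. Neither has a category for no LHON mutation.

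On timing and consequences, protocol 6.1 says of the genotype: "The report from the genetic analysis will need to be on file prior to Visit 4". It then says: "Should the genetic diagnosis reveal that a patient does not harbour a LHON-specific mtDNA mutation, the patient will be withdrawn from the study".

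On use, SAP 12 assigns comparisons with natural history to mITT, which requires one of the three major mutations. LEROS-only outcomes stay in ITT. For off-chart improvement, for example, SAP 12.2 says: "This endpoint will be analysed by means of descriptive statistics in the LEROS ITT population". The recovery and Kaplan-Meier analyses in 12.3 and the nadir table in 11.2.2 use the same set. SAP 14 declares no deviations from the protocol.

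**The concern.** A programmer cannot satisfy all of these sections. Under 5.4 the other-mutation subgroup would be empty. Under 8.2 anyone enrolled with one follow-up acuity counts, whatever the genetic test shows. Widening ITT to rarer LHON mutations looks deliberate, because the protocol does not withdraw those carriers and 9.3 gives them a subgroup. Nothing suggests an intention to keep patients whom the protocol withdraws for having no LHON-specific mutation, yet 8.2 admits them.

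At stake is what some descriptive outputs mean. Visual loss without a LHON mutation need not follow the course of LHON. An early improvement in such an eye would be counted as a recovery on idebenone in LHON, and an eye that does not improve would sit in the risk set until censored.

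**Working it through.** **1. Can such a patient enter ITT?** Genotype is not needed for enrolment (SAP 5.4; protocol 4.1). Acuity is measured at every visit, including Months 1 and 3 (protocol 6.2). The report is due before Visit 4, which is Month 6. Up to two scheduled on-treatment acuities can therefore precede the result. Withdrawn patients are also asked to complete the Visit 9 evaluations if possible (protocol 6.5.1). One post-baseline acuity satisfies SAP 8.2. The SAP overrides the protocol where they differ (SAP 2; protocol 9.1), so protocol 9.3.1 does not remove the patient.

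**2. Which outputs can the patient reach?** This assumes the genetic deadline is kept and withdrawal follows promptly.

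| Output | Reached? | Reason |
|---|---|---|
| Any-time recovery and Kaplan-Meier (SAP 12.3) | Yes | Early event, or censored at last on-treatment assessment |
| Nadir (SAP 11.2.2) | Yes | Any eye with follow-up acuity contributes |
| Acuity categories, early visits (SAP 4.2, 12.2) | Yes | Reported at each assessment time point |
| Plain recovery row, Tables 12-5 and 12-6 | Possibly | Counts eyes or patients with a Visit 9 acuity |
| On-treatment tables, Months 12 to 24 | No | No such visit; missing data are left out (SAP 9.1) |
| Recovery-maintenance rows | No | Need recovery at 24 months |
| Three named-mutation subgroups | No | Patient carries none of them |
| Comparisons with natural history | No | mITT under SAP 12 |

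Visit 9 acuity does not feed the Kaplan-Meier curves, because these use months in treatment and censor at the last on-treatment assessment.

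**3. Does the sample size move?** No. The plan's figure is 110 evaluable LEROS eyes (40% against 22%, 90% power, two-sided 0.05). The allocation is not stated, so I take ρ = 175/110 = 1.591 from the 175 natural-history eyes:

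- pooled rate p̄ = (0.40 + 1.591 × 0.22)/2.591 = 0.2895
- n = [1.960 × √(1.6286 × 0.2895 × 0.7105) + 1.2816 × √(0.24 + 0.1716/1.591)]² / 0.18² = (1.134 + 0.756)² / 0.0324 ≈ 110.3, or 111 rounded up
- power with 110 against 175 eyes = 89.9%
- 110/0.70 = 157.1, so 158 eyes or 79 patients, against the stated 80

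The plan's figure reproduces. It concerns an mITT comparison, so the ITT definition leaves it unchanged.

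**4. How large could the effect be?** The documents give neither the number of mutation-negative patients nor their recovery rate. Let k of N patients be mutation-negative with rate r, and let carriers have rate 0.40. That is the plan's assumed LEROS responder rate for the composite primary endpoint, borrowed here as a placeholder. Then

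observed rate = [(N − k) × 0.40 + k × r]/N, so shift = k × (r − 0.40)/N.

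Taking r from 0 to 1:

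| k | N = 80 (one onset stratum) | N = 160 (all) |
|---|---|---|
| 1 | -0.5 to +0.75 points | -0.25 to +0.375 |
| 2 | -1.0 to +1.5 | -0.5 to +0.75 |
| 4 | -2.0 to +3.0 | -1.0 to +1.5 |
| 8 | -4.0 to +6.0 | -2.0 to +3.0 |

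For example, k = 8, N = 80, r = 1 gives (72 × 0.40 + 8)/80 = 36.8/80 = 46.0%. All patients are treated as evaluable, so these are outer limits for each k.

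**The case against.** The strongest reply is that the SAP is not silent on genotype. Section 5.4 attaches three-mutation confirmation to ITT, and 8.4 builds a three-mutation control set partly on the patients in ITT. That stands: it would be wrong to say the SAP has no genetic criterion for ITT. It does not cure 8.2, because the operative definition and the other-mutation subgroup point the other way.

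The reply also limits the reach, and rightly. A reader might infer that every LEROS-only recovery analysis, or even the primary result, is contaminated. The table above does not support that. No natural-history comparison is touched, and the exposed outputs are descriptive. SAP 8.2 to 8.4 and SAP 12 disagree about whether ITT or mITT serves the natural-history comparisons, but a patient withdrawn before Month 6 has no Month 12 acuity for the primary analysis in either set.

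A reader might also expect the recovery rate to be inflated, or the other-mutation column to be badly distorted. The documents give no recovery rate for these patients, so the direction is unknown. A patient with no LHON mutation does not fit the label "Any other mutation", so placement in that column cannot be assumed. The contrast among the three named mutations is intact.

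Numbers should be small, because entry requires visual loss attributed to LHON with other eye disease excluded. SAP 10.1 lists discontinuation reasons, population flags and patients without major-mutation confirmation at baseline, so these patients can be identified. A listing does not exclude them, however.

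Finally, the missing one-dose condition is not an error in itself. A set without it is arguably closer to intention to treat.

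**Conclusion.** The point holds as a contradiction between definitions with a limited consequence. SAP 8.2 conflicts with SAP 5.4 and protocol 9.3.1. As written, it lets mutation-negative patients whom the protocol withdraws enter the any-time recovery and Kaplan-Meier analyses, nadir, early-visit categories and possibly the plain Visit 9 recovery row.

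Under the stated assumptions the shift is between -4.0 and +6.0 points at the extreme (8 of 80), and no more than -1.0 to +1.5 points for two or fewer of 80. The true count could be zero.

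The conclusion rests on three assumptions: the genetic deadline is kept, SAP 12 governs which set serves the natural-history comparisons, and protocol version 3.0, which SAP 14 cites, has the same ITT definition as the version 2.1 supplied. Protocol 3.1 says the versions are very similar or identical. On that footing the no-deviations statement in SAP 14 is wrong on this point.

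**What to change.** - In SAP 8.2, require a confirmed LHON-specific mtDNA mutation, one of the three major ones or another, for ITT.
- Amend SAP 5.4 to agree with 8.2.
- In SAP 9.3 and Table 19-3, define the other-mutation group as confirmed other LHON mutations only.
- Keep mutation-negative patients in the Safety population, report how many there were, and list their acuity separately.
- Declare the change from protocol 9.3.1 in SAP 14.

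Genotype is fixed before treatment and cannot be altered by it, so excluding patients on it does not select on response. Restoring the one-dose condition is optional. The cost is wording and one flag from genetic results the protocol already requires on file. The downside is a few patients fewer in the LEROS-only tables.

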8.3 Modified Intent-to-Treat Population

Modified Intent-to-Treat (mITT) population will include all patients enrolled to LEROS, who are carriers of only one of the three major LHON mtDNA (G11778A, G3460A or T14484C), received at least one dose of the study medication and provide at least one post-BL VA assessment.

The mITT population in conjunction with the external NH control set defined in section 8.4, will be used as a sensitivity analysis of the evaluation of efficacy endpoints defined in section 4.

8.4 Natural History control set

The Natural History (NH) external control set for LEROS study is constituted by the combined data from CRS-1 and CRS-2. In order to ensure comparability between populations, the following criteria, based on LEROS inclusion/exclusion (section 5.4 and 5.5) criteria and patients included in the ITT population, are required for subjects to be included in the external NH (Natural History) control set out of all patients included in CRS-1 and CRS-2:

SNT-IV-005 Statistical Analysis Plan

Confidential

- Carriers of only one of the three major LHON mtDNA (G11778A, G3460A or T14484C)
- Age \geq 12 years;
- No other cause of visual impairment apart from LHON;
- Date of symptoms onset is defined (or at least month and year known);
- Onset of symptoms are less or equal to 5 years at BL visit;
- At least 2 VA assessments;
- VA assessments visit date must be defined (or at least month and year known).

The NH control set in conjunction with the ITT population will be used to evaluate efficacy endpoints defined in section 4.

